10.4.2 Analysis of the Secondary Endpoint(s)

- FSFI score (see attached below):
 - Definition: 19 question survey
 - Graded responses from 0 to 5
 - Single endpoint measure with a score that can range from 0 to 95
- VSI score (see attached below):
 - Definition: 19 question survey
 - Graded responses from 0 to 3
 - Single endpoint measure with a score that can range from 0 to 15
- Vaginal pH
 - Definition: pH number
 - Interval variable ranging from 0 to 14
 - Single endpoint
- Vaginal maturation index (VMI)
 - Definition: microscopic analysis of vaginal tissue that assigns a percentage to the amount of parabasal, intermediate, and squamous cells visualized that add up to 100%

CONFIDENTIAL

This material is the property of the NYU School of Medicine and Langone Medical Center. Do not disclose or use except as authorized in writing by the study sponsor
Interventional Template Version: 11 January 2019

- Ratio variable ranging from 0 to 100
- Single endpoint (only the % of squamous cells will be reported since that is most closely correlated with hormonal influence on the vaginal tissue)
- Visual analog scale (VAS) score for dyspareunia, itching, dryness
 - Definition: visual scale attempting to capture the intensity of a symptom
 - Ratio variable ranging from 0 to 10
 - Single endpoint
- Vaginal rugal folds
 - Definition: visualization of the presence of vaginal rugal folds on pelvic exam
 - Continuous variable
 - Single endpoint

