Appendix 1. Female Sexual Function Index Scoring

Question	Response Options
1. Over the past 4 weeks, how often did you feel sexual desire or interest?	5 = Almost always or always 4 = Most times (more than half the time) 3 = Sometimes (about half the time) 2 = A few times (less than half the time) 1 = Almost never or never
2. Over the past 4 weeks, how would you rate your level (degree) of sexual desire or interest?	5 = Very high 4 = High 3 = Moderate 2 = Low 1 = Very low or none at all
3. Over the past 4 weeks, how often did you feel sexually aroused ("turned on") during sexual activity or intercourse?	0 = No sexual activity 5 = Almost always or always 4 = Most times (more than half the time) 3 = Sometimes (about half the time) 2 = A few times (less than half the time) 1 = Almost never or never
4. Over the past 4 weeks, how would you rate your level of sexual arousal ("turn on") during sexual activity or intercourse?	0 = No sexual activity 5 = Very high 4 = High 3 = Moderate 2 = Low 1 = Very low or none at all
5. Over the past 4 weeks, how confident were you about becoming sexually aroused during sexual activity or intercourse?	0 = No sexual activity 5 = Very high confidence 4 = High confidence 3 = Moderate confidence 2 = Low confidence 1 = Very low or no confidence
6. Over the past 4 weeks, how often have you been satisfied with your arousal (excitement) during sexual activity or intercourse?	0 = No sexual activity 5 = Almost always or always 4 = Most times (more than half the time) 3 = Sometimes (about half the time) 2 = A few times (less than half the time) 1 = Almost never or never

CONFIDENTIAL

This material is the property of the NYU School of Medicine and Langone Medical Center. Do not disclose or use except as authorized in writing by the study sponsor
Interventional Template Version: 11 January 2019

7. Over the past 4 weeks, how **often** did you become lubricated ("wet") during sexual activity or intercourse?

0 = No sexual activity
5 = Almost always or always
4 = Most times (more than half the time)
3 = Sometimes (about half the time)
2 = A few times (less than half the time)
1 = Almost never or never

8. Over the past 4 weeks, how **difficult** was it to become lubricated ("wet") during sexual activity or intercourse?

0 = No sexual activity
1 = Extremely difficult or impossible
2 = Very difficult
3 = Difficult
4 = Slightly difficult
5 = Not difficult

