9. Over the past 4 weeks, how often did you **maintain** your lubrication ("wetness") until completion of sexual activity or intercourse?

0 = No sexual activity
5 = Almost always or always
4 = Most times (more than half the time)
3 = Sometimes (about half the time)
2 = A few times (less than half the time)
1 = Almost never or never

10. Over the past 4 weeks, how **difficult** was it to maintain your lubrication ("wetness") until completion of sexual activity or intercourse?

0 = No sexual activity
1 = Extremely difficult or impossible
2 = Very difficult
3 = Difficult
4 = Slightly difficult
5 = Not difficult

11. Over the past 4 weeks, when you had sexual stimulation or intercourse, how **often** did you reach orgasm (climax)?

0 = No sexual activity
5 = Almost always or always
4 = Most times (more than half the time)
3 = Sometimes (about half the time)
2 = A few times (less than half the time)
1 = Almost never or never

12. Over the past 4 weeks, when you had sexual stimulation or intercourse, how **difficult** was it for you to reach orgasm (climax)?

0 = No sexual activity
1 = Extremely difficult or impossible
2 = Very difficult
3 = Difficult
4 = Slightly difficult
5 = Not difficult

13. Over the past 4 weeks, how **satisfied** were you with your ability to reach orgasm (climax) during sexual activity or intercourse?

0 = No sexual activity
5 = Very satisfied
4 = Moderately satisfied
3 = About equally satisfied and dissatisfied
2 = Moderately dissatisfied
1 = Very dissatisfied

14. Over the past 4 weeks, how **satisfied** have you been with the amount of emotional closeness during sexual activity between you and your partner?

0 = No sexual activity
5 = Very satisfied
4 = Moderately satisfied
3 = About equally satisfied and dissatisfied
2 = Moderately dissatisfied
1 = Very dissatisfied

15. Over the past 4 weeks, how **satisfied** have you been with your sexual relationship with your partner?

5 = Very satisfied
4 = Moderately satisfied
3 = About equally satisfied and dissatisfied
2 = Moderately dissatisfied
1 = Very dissatisfied

16. Over the past 4 weeks, how **satisfied** have you been with your overall sexual life?

5 = Very satisfied
4 = Moderately satisfied
3 = About equally satisfied and dissatisfied
2 = Moderately dissatisfied
1 = Very dissatisfied

17. Over the past 4 weeks, how **often** did you experience discomfort or pain during vaginal penetration?

0 = Did not attempt intercourse
1 = Almost always or always

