2 = Most times (more than half the time)
3 = Sometimes (about half the time)
4 = A few times (less than half the time)
5 = Almost never or never

18. Over the past 4 weeks, how **often** did you experience discomfort or pain following vaginal penetration?

0 = Did not attempt intercourse
1 = Almost always or always
2 = Most times (more than half the time)
3 = Sometimes (about half the time)
4 = A few times (less than half the time)
5 = Almost never or never

19. Over the past 4 weeks, how would you rate your **level** (degree) of discomfort or pain during or following vaginal penetration?

0 = Did not attempt intercourse
1 = Very high
2 = High
3 = Moderate
4 = Low
5 = Very low or none at all

CONFIDENTIAL

19h Vaginal Symptom Index

Vaginal Symptom Index Score

1. Vaginal dryness

0=none
1=mild
2=moderate
3=severe

2. Vaginal soreness

0=none
1=mild
2=moderate
3=severe

3. Vaginal irritation

0=none
1=mild
2=moderate
3=severe

4. Vaginal discharge

0=none
1=mild
2=moderate
3=severe

5. Dyspareunia

0=none
1=mild
2=moderate
3=severe

19i Patient Global Impression of Improvement

Check the number that best describes how your post-intervention condition is now, compared with how it was before the intervention:

Very much better = 1

Much better = 2

A little better = 3

No change = 4

A little worse = 5

Much worse = 6

Very much worse = 7

CONFIDENTIAL

This material is the property of the NYU School of Medicine and Langone Medical Center. Do not disclose or use except as authorized in writing by the study sponsor
Interventional Template Version: 11 January 2019

20 Schedule of Events

Activity	Visit 1 (Day 0)	Visit 2 (12 weeks +/- 1 week)
Study team procedures		
Routine history of present illness, medical, obstetrical, gynecological, surgical, medication, HRT usage history	X	
Vitals and routine physical exam including pelvic	X	X
GSM Diagnosis	X	
Consent	X	
VAS score for dyspareunia, itching, and dryness	X	X
Rugal fold presence	X	X
VSQ, FSI, VSI	X	X
Randomization	X	
Study drug/device dispensation	X	
Participant study drug/device compliance check		X
Check for side-effects and/or AE due to study agent		X
Laboratory Assessments		
Urine pregnancy test	X	
Urine analysis	X	
Vaginal pH	X	X
VMI	X	X

CONFIDENTIAL

This material is the property of the NYU School of Medicine and Langone Medical Center. Do not disclose or use except as authorized in writing by the study sponsor
Interventional Template Version: 11 January 2019

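### The FSFI score implied by the plan counts no sexual activity and no attempted intercourse as worse than the worst function, and its true minimum is 4, not 0

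*Combined protocol and SAP*

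**What the plan says.** Section 10.4.2 describes the FSFI in three lines: "Definition: 19 question survey", "Graded responses from 0 to 5" and "Single endpoint measure with a score that can range from 0 to 95". It gives no domain scores, no weights and no rule for women who are sexually inactive.

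The form in attachment 19g (Appendix 1, Female Sexual Function Index Scoring) is more specific:

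- Items 3 to 14 carry the option "0 = No sexual activity".
- Items 17 to 19 carry "0 = Did not attempt intercourse".
- On all 15 of these items the worst rating is 1 and the best is 5.
- Items 1, 2, 15 and 16 (the two desire items, satisfaction with the sexual relationship, and satisfaction with sexual life overall) run from 1 to 5 with no zero option.

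Section 10.4 sends continuous measures into a linear mixed model for the 12-week mean, unadjusted and adjusted for baseline. It expects no further covariates and keeps all participants in the analysis. Section 4.2.2 lists change in this score among the secondary endpoints (abbreviated there as FSI), and section 10.2 expects it to improve.

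**The concern.** A zero on 15 of the 19 items says that the question did not apply in the past four weeks. It does not grade how badly a woman functions. Added into a total, it acts as a severity grade one step below the worst real answer. The pain items show this most plainly: a woman who avoids intercourse gets 0 on items 17 to 19 together, while one who attempts it with the worst rating on all three gets 3.

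The trial can be expected to include such women. No criterion in section 5.1 requires sexual activity, and the VSQ in attachment 19a ends early for women who are not sexually active with a partner. The FSFI total would therefore reflect two things at once: whether a woman was active before each visit, and how she functioned if she was. Adjusting for the baseline score does not remove the contribution of a woman whose status changes between visits.

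Sections 10.1, 10.2 and 10.5 say that the pilot is meant to supply estimates and their variability for a larger trial. An FSFI mean and SD that combine activity with function would be carried into that planning without any sign of the mixture.

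**Working it through.** **Inputs.** From section 10.4.2: 19 items, graded 0 to 5, total 0 to 95. From attachment 19g: items 3 to 14 (12 items) and items 17 to 19 (3 items) have a zero option, 15 in all; items 1, 2, 15 and 16 (4 items) do not. From sections 5.6 and 10.5: 60 randomized, 30 per arm, with 40 evaluable expected at 12 weeks. An equal split of the 40, giving 20 per arm, is an assumption.

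**The plan's own figure.** 19 × 0 = 0 and 19 × 5 = 95. The stated range is reproduced exactly by an unweighted sum with every item coded 0 to 5.

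**The range on the attached form.** Minimum: 4 × 1 + 15 × 0 = 4. Maximum: 19 × 5 = 95. Totals of 0 to 3 cannot occur on a completed form; the upper end is correct.

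**Range by status over the four-week recall period.**

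| Status | Items 1, 2, 15, 16 | Items 3–14 | Items 17–19 | Total |
|---|---|---|---|---|
| All 15 zero-option items at 0 | 4 to 20 | 0 | 0 | 4 to 20 |
| Active, intercourse not attempted | 4 to 20 | 12 to 60 | 0 | 16 to 80 |
| Every item rated 1 to 5 | 4 to 20 | 12 to 60 | 3 to 15 | 19 to 95 |

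**Effect of one change of status.** Hold items 1, 2, 15 and 16 fixed and move a woman from all zeros to a uniform rating r on the 15 items. The gain is 15 × r:

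- worst rating, r = 1: 15 points
- middle rating, r = 3: 45 points
- best rating, r = 5: 75 points

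**Effect on an arm mean.** One net switch in an arm of n women moves the mean by 15r / n:

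- n = 20: 15/20 = 0.75, 45/20 = 2.25, 75/20 = 3.75
- n = 30: 15/30 = 0.5, 45/30 = 1.5, 75/30 = 2.5

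These figures are per net switch. The documents give no proportion inactive at baseline, no rate of switching, and no FSFI effect size or SD, so the total shift to expect cannot be computed from them.

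**The case against.** Several counter-arguments have force.

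**The sum is inferred.** Section 10.4.1 says outright that VSQ answers are added up; section 10.4.2 does not say so for the FSFI. That is correct, but a single score of 0 to 95 from 19 items graded 0 to 5 is the unweighted sum, and the plan offers no other scoring rule.

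**Moving from inactive to active may be the benefit sought.** This stands. A reader might infer that a shift of 0.75 to 3.75 points would arise with no change in function. The documents do not support that: function on the 15 items is unobserved while a woman is inactive, so nobody can say it was unchanged. The 75-point end also requires the best rating on every one of those items.

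**Nothing shows that the mixture dominates.** A reader might infer that a few switches would swamp a treatment effect, or that the SD will be inflated by a known amount. Without an effect size, an SD or a switching rate in the documents, neither can be shown.

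**The range error is small.** Also true: only totals of 0 to 3 are ruled out. Nor is it right that every sexually active woman scores at least 19, because one who did not attempt intercourse can score as low as 16.

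**Excluding women with zero codes has its own cost.** It might seem natural to call the whole FSFI not evaluable whenever a zero code appears. That would discard 16 answered items from a woman who is active but avoids intercourse, perhaps because it hurts. It would also select on status after randomisation and depart from the all-participant analysis in sections 10.3 and 10.4. This argues against exclusion as the only analysis. It does not argue for leaving the planned score as the only summary.

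**Conclusion.** Wrong as written. The scoring implied by section 10.4.2 does not match the attached form. The attainable minimum is 4, and 15 of the 19 items use 0 for a state that is not a function rating. As planned, the score ranks a woman with no activity below one with the worst function on every item, and the FSFI mean, SD and confidence interval combine activity status with function.

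The size is 15 to 75 points for one woman moving from all zeros to fully rated, or 0.75 to 3.75 points on the mean of a 20-woman arm per net switch. This rests on the inferred unweighted sum, on the four remaining items staying the same, and on 20 evaluable women per arm. How many women switch is unknown, and part of any shift may be genuine improvement.

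The consequence is limited to the interpretation of one secondary endpoint in a descriptive pilot, and to its use in planning the next trial. The VSQ primary endpoint and the precision statement in section 10.5 do not depend on it.

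**What to change.** In section 10.4.2:

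1. State that the FSFI score is the unweighted sum of the 19 items, if that is intended, and correct its range to 4 to 95.
2. Keep the all-participant score as planned. Beside it, report the proportion sexually active and the proportion who attempted intercourse, by arm and visit, as separate lines.
3. Add a supporting FSFI summary that does not count the activity codes as severity. One form is to summarise women with no zero codes at either visit, handling items 17 to 19 separately from items 3 to 14, so that women who were active but did not attempt intercourse keep their answered items. Show the numbers excluded by arm.

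The cost is SAP wording and a few table rows; the form already collects everything needed. The supporting summary will have a smaller denominator and is partly defined by status after randomisation. It should be labelled as such and should not replace the all-participant analysis.

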4.2.2 Secondary Study Endpoints

The secondary study endpoints will include: the change in the FSI and VSI score from baseline to the 12 week visit, the change in the percentage of superficial squamous cells in the vaginal maturation index, the change in vaginal pH, the qualitative change in rugal fold appearance, and the change in VAS scoring for vaginal dyspareunia, itching, and dryness. These are well-studied measurement tools for GSM research and have been used in some combination in all of the studies cited earlier.

Vaginal pH in a postmenopausal woman is generally between 6.0 and 8.0, while an estrogenized vagina will have a pH of 3.5 to 4.5 (18). Thus, the change in pH can be a surrogate marker for the hormonal influence on vaginal epithelium.

VMI is a qualitative measure of hormonal influences on the vaginal epithelium. It measures the percentage of parabasal, intermediate, and superficial squamous cells appearing on a smear and is a valuable tool when comparing the changes in two samples of the same patient (14).

Patient global impression of improvement (PGI-I), a one question assessment, will also be asked at the follow up visit for overall patient satisfaction assessment.

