7.2.3 Enrollment/Baseline

Screening/Enrollment/Baseline Visit (Visit 1, Day 0)

- Obtain informed consent of potential participant verified by signature on study informed consent form
- Obtain demographic information, history of present illness, medical history, surgical history, obstetrical history, gynecologic history, medication history, HRT usage history
- Perform physical exam: vitals, cardiovascular, abdominal, pelvic
- Diagnose GSM
- If GSM diagnosis, explain study and verify inclusion and exclusion criteria
- Obtain urine pregnancy test: result must be negative and available prior to administration of study agents

CONFIDENTIAL

This material is the property of the NYU School of Medicine and Langone Medical Center. Do not disclose or use except as authorized in writing by the study sponsor
Interventional Template Version: 11 January 2019

- Obtain urine analysis: result must be negative and available prior to administration of study agents
- Record VAS scores for dyspareunia, itching, and dryness
- Record rugal fold analysis
- Collect pelvic samples for vaginal pH and vaginal tissue scraping for VMI
- Have patient fill out VSQ, FSFI, VSI
- Perform randomization and determine patient study arm
- Give patient appropriate prescription (HLA vs vaginal estrogen)
- Counsel on medication dosage, usage, and application
- Counsel on communication routes to inform research team about side effects and/or AE

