10.2 Statistical Hypotheses

We expect no clinically meaningful differences in baseline characteristics or baseline assessment of outcomes between those randomized to HLA or to vaginal estrogen, however this is possible given the limited pilot trial sample size. These differences will be assessed and considered in the evaluation of outcomes for primary and secondary endpoints.

We expect a clinically meaningful improvement in the change measured at 12 weeks (comparison of VSQ at 12 weeks, adjusted for baseline) in VSQ in the HLA group, and expect this to be greater as compared to those randomized to vaginal estrogen. Similarly, we expect to observe clinically meaningful improvements in the HLA group at 12 weeks, beyond those observed in those randomized to the vaginal estrogen cohort. These include VSI, FSFI, VAS for dyspareunia, itching, and dryness, vaginal pH, and presence of rugal folds.

CONFIDENTIAL

This material is the property of the NYU School of Medicine and Langone Medical Center. Do not disclose or use except as authorized in writing by the study sponsor
Interventional Template Version: 11 January 2019

These estimates will provide estimates for establishing effectiveness in future trials.

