10.4 Description of Statistical Methods

Baseline (pre-randomization) participant demographics and clinical characteristics will be summarized through descriptive statistics overall, and by randomized group. Clinical characteristics will include past HRT use, uterus present or not, and components of their medical and gynecologic history. Details of each outcome measure is provided below. Analysis of the primary and secondary measures will include summarizing each by the mean and standard deviation at baseline and all measured time points, including at the primary outcome time of 12 weeks. For continuous measures, a linear mixed effects regression model will estimate the mean outcome at 12 weeks, both unadjusted and adjusted for baseline measurement. No further adjustment for participant characteristics is expected given the limited trial size. The linear mixed effects regression model will allow all participants to be included in analysis, regardless of completion of study follow up at 12 weeks, under the assumption of this assessment being missing at random.

Missing outcome data will be summarized by participant characteristics to understand how to better retain individuals in treatment.

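### Rugal folds are defined by presence but typed as continuous with no scale, so the plan sends an apparently yes/no endpoint to a mean, an SD and a linear mixed model

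*Combined protocol and SAP*

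**What the plan says.** Section 10.4.2 defines the endpoint as "visualization of the presence of vaginal rugal folds on pelvic exam" and, on the next line, types it "Continuous variable". In the same list, pH, maturation index and VAS each have a numeric range; rugal folds have none.

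Other sections describe the endpoint as follows:

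- Section 10.2 lists "vaginal pH, and presence of rugal folds" among the expected improvements.
- Section 20 (Schedule of Events) has "Rugal fold presence" at both visits.
- Section 4.2.2 has "the qualitative change in rugal fold appearance".
- Section 7.2.3 (baseline visit) says only "Record rugal fold analysis".
- Section 7.2.4 (final visit) does not name rugal folds, although Section 20 schedules them there.

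Section 10.4 sets the analysis for primary and secondary measures: "summarizing each by the mean and standard deviation at baseline and all measured time points". It continues: "For continuous measures, a linear mixed effects regression model will estimate the mean outcome at 12 weeks", both unadjusted and adjusted for baseline. No method is named for a binary or ordinal outcome. Section 10.1 plans estimates with 95% CIs and says that formal comparison of the arms is not the emphasis.

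**The concern.** The type label decides the analysis. A finding that is seen or not seen has no natural mean and SD beyond its proportion, and a model with normal errors and a common variance does not describe it. Followed literally, the plan would report rugal folds with symmetric normal-theory intervals in arms of about 20 women.

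Such intervals can under-cover, can run below 0% or above 100%, and can shrink to nothing when all women have the same finding. Section 10.2 says that the estimates are meant to inform later trials, so a misleading interval would carry forward. There is also a data-quality risk: with no coding defined, examiners may record different things, and that cannot be repaired afterwards.

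**Working it through.** **Inputs.** Sections 5.6 and 10.5 give 60 enrolled and 40 evaluable at 12 weeks; Section 10.6.1 gives 1:1 allocation. So n = 40/2 = 20 evaluable per arm (30 randomized). The documents give no rugal fold prevalence, so every rate below is an assumption, shown over a range.

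**The plan's only precision figure** (Section 10.5: 95% CI width 1.7 with at least 80% probability, 30 per arm, SD 2) does not concern rugal folds, but it shows which interval the plan has in mind. Width = 2·t(0.975, 29)·s/√30, with s = 2·√(35.14/29) = 2.20 at the 80th percentile, gives 2 × 2.045 × 2.20/5.477 = 1.64. The probability of a width of at most 1.7 is 86.8%, so the figure holds for the mean of one arm. For the arm difference the probability is 2.8%. The planned precision is therefore per arm.

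**Method.** Code presence as 1 and absence as 0, and apply the pooled-variance linear model. With two visits and complete data, this stands in for the planned mixed model. The pooled variance s² is the average of the two arms' p(1−p)·n/(n−1).

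- Arm difference: (p1 − p2) ± t(0.975, 38)·√(2s²/20)
- One arm: p ± t(0.975, 38)·√(s²/20)

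Coverage comes from exact enumeration of all binomial outcomes.

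| True rates, n = 20 per arm | Linear CI, difference | Newcombe CI, difference | Linear CI, first arm |
|---|---|---|---|
| 0.5 / 0.5 | 95.7% | 95.7% | 95.8% |
| 0.5 / 0.3 | 94.7% | 94.5% | 94.1% |
| 0.3 / 0.1 | 94.4% | 96.1% | 89.8% |
| 0.2 / 0.1 | 94.3% | 96.5% | 88.7% |
| 0.4 / 0.05 | 94.5% | 96.1% | 86.6% |
| 0.9 / 0.6 | 93.8% | 95.2% | 99.7% (second arm 88.8%) |
| 0.05 / 0.05 | 98.8% | 99.8% | 85.9% |
| 0.95 / 0.9 | 91.9% | 98.6% | 94.9% (second arm 86.5%) |
| 0.1 / 0.02 | 87.1% | 99.1% | 84.7% |

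With 30 per arm, the linear CI for the difference covers 93.0% to 97.2% over all pairs tried.

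**Baseline-adjusted version** (20,000 simulated trials per setting, 20 per arm). Coverage for the difference is 94.3% to 95.0% in four moderate settings and 98.5% in a rare-outcome setting with equal arms. It is 86.6% in a rare-outcome setting with unequal arms (5% present at baseline, 95% of these persisting, new presence in 2% versus 10%).

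**Limits outside 0 to 100%.** This happens to the first arm's interval in 74% of trials at 0.1/0.1 and 93% at 0.9/0.6. An example is 18/20 versus 12/20. The arm variances are 0.0947 and 0.2526, so s² = 0.1737. The first arm's interval is 0.90 ± 2.024 × √(0.1737/20) = 0.90 ± 0.189, or 71.1% to 108.9%. Wilson gives 69.9% to 97.2%.

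**Uniform findings.** At 20/20 a t-interval from that arm alone has zero width; Wilson gives 83.9% to 100%. In the pooled model the standard error is zero only when both arms are uniform, which happens in 12.9% of trials at 0.05/0.05.

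**The case against.** A reader might infer that the planned model makes the confidence intervals for this endpoint invalid throughout. The documents and the arithmetic do not support that. On a 0/1 outcome the linear model estimates a risk difference, and its interval for the arm difference is close to nominal at moderate rates, sometimes closer than Newcombe's, which can be conservative. Failure needs rates near 0 or 1, and no prevalence is given to say that this will happen. Even a t-interval from one arm's own SD covers 95.9% at a rate of 0.5 and 94.7% at 0.3; it drops to 92%, 88% and 64% only at 0.80, 0.90 and 0.95.

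A reader might also take present/absent coding as stated. It is a strong inference from Sections 10.2, 10.4.2 and 20, but no coding is written down. Sections 4.2.2 and 7.2.3 leave room for a grade, and the word qualitative settles nothing, since Section 4.2.2 also applies it to the maturation index, which is a percentage.

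The mixed model also has merits that a simple week-12 proportion lacks: it adjusts for baseline and, under missing at random, keeps women without a week-12 visit. With 33% loss assumed, that is a real cost. Finally, this is one secondary endpoint in a pilot, and it drives neither the sample size nor any decision rule.

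All of this stands and limits the point. It does not remove the contradiction: neither a yes/no finding nor an undefined grade is continuous, and the plan offers no other method.

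**Conclusion.** The point holds in a limited form. The type label conflicts with the endpoint's own definition, and under Section 10.4 that label routes an apparently binary finding to an ill-fitting summary and model.

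The effect on the treatment-effect interval is small at moderate rates (about 94% to 96% coverage) and material only near 0 or 1 (92% at 0.95/0.9, 87% at 0.1/0.02). The effect on per-arm intervals is larger: 86% to 89% at 0.05/0.05, 0.4/0.05 and 0.2/0.1, with limits that often leave the possible range. Those intervals carry weight because Section 10.1 is built on estimating outcomes in the hyaluronic acid arm.

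These figures assume 0/1 coding, 20 evaluable women per arm, complete data for those women, and the rates shown, none of which comes from the documents. The correction is worth making because the misfit is plain and cheap to remove, not because it threatens the trial's main result.

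**What to change.** In Section 10.4.2, replace the continuous label for rugal folds with binary (present/absent). In Section 10.4, exempt this endpoint from the mean/SD and linear mixed model rule. State that it is reported as n/N by arm and visit with Wilson 95% CIs, and as a week-12 risk difference with a Newcombe 95% CI.

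That primary report is unadjusted and uses completers only. If the data allow, add a supportive baseline-adjusted logistic or GEE model that uses both visits, so that all randomized women contribute. State its missing-data assumption, since an unweighted GEE needs a stronger one than the missing-at-random assumption in Section 10.4. Accept that the model may not be estimable if the finding is rare or nearly universal.

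If the examination is in fact graded, define the levels in Section 10.4.2 and use an ordinal summary instead; forcing a grade into two categories would lose information. Align the wording of Sections 4.2.2, 7.2.3 and 20 with the chosen coding, and reconcile the final-visit list in Section 7.2.4 with Section 20.

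The cost is a few lines of text and standard software. The coding should be settled before data are recorded.
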